6.1.2.2 Concomitant Medications/Measures

All concomitant medications and measures will be captured in the source documents. Only those medications that the patient is taking at baseline on a routine basis or medications that cause an AE will be captured (e.g., onetime medications, PRN medications, supportive medications, electrolyte replacement and medications given to treat adverse events will not be captured).

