1.1.2 Secondary Objectives

- To examine if oral DAC-THU modulates DNA methylation, as well as gene, micro-RNA, and endogenous retroviral expression profiles of NSCLC, EsC, and MPM cells and alters the tumor micro-environment.
- To examine if oral DAC-THU modulates plasma tumor DNA methylation, circulating tumor cells and peripheral immune subsets.

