3.3.4 Dosage Modification and Management of Immune-Related Adverse Events

Since inhibition of PD-L1 stimulates the immune system, irAEs may occur. Treatment of irAEs is mainly dependent upon severity (NCI-CTCAE grade):

- Grade 1 to 2: treat symptomatically or with moderate dose steroids, more frequent monitoring.
- Grade 1 to 2 (persistent): manage similar to high grade AE (Grade 3 to 4).
- Grade 3 to 4: treat with high dose corticosteroids.

Treatment of irAEs should follow accepted guidelines set forth in Table 10.

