4 CONCOMITANT MEDICATIONS/MEASURES

4.1 HEMATOLOGIC AND BLOOD PRODUCT SUPPORT

Blood product support should be provided to maintain platelets > 20,000 cells/mcl, Hgb > 8.0 gm/dl and as clinically indicated. Growth factor support is not permitted with exception of administration of filgrastim. Filgrastim will not be administered prophylactically, but may be administered if a patient experiences neutropenic sepsis, or if clinically indicated.

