4.3 ELECTROLYTE REPLACEMENT

Electrolyte replacement will be provided to maintain serum levels within normal limits.

4.4 **PROTON PUMP INHIBITORS**

Given the uncertainties regarding effects of proton pump inhibitors on absorption of DAC-THU, proton pump inhibitors will not be used except on days when DAC-THU is not administered.

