5.1.3 Immune Subset Analyses

Peripheral blood mononuclear cells (PBMC) will be assessed using multiparameter flow cytometry for immune subsets including but not necessarily limited to Tregs, MDSC, effector and exhausted CD4+ or CD8+ T-cells, and CD14+ monocytes. Assessment will include functional markers, i.e. PD-1, PD-L1, Tim-3, CTLA-4, HLA-DR and/or CD40. Samples will be drawn (as indicated in **Appendix 4**) and picked up by the [name] Lab (see Section **5.2.4**) for analysis. The [name] Lab will prepare the samples for staining, stain and run the samples by multiparametric flow cytometry (MACSQuant, Miltenyi Biotec, Bergisch Gladbach, DE), and analyze the data using FlowJo (FlowJo LLC, Ashland, OR) software.

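### On-study steroids, other immunosuppressants and filgrastim stay in source documents only (Section 6.1.2.2), and Section 10 has no rule for immune-subset, CTC or blood-count samples drawn under them

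*Combined protocol and SAP*

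**What the plan says.** Section 6.1.2.2 has two tiers. The first is complete: "All concomitant medications and measures will be captured in the source documents". The second is narrow: "Only those medications that the patient is taking at baseline on a routine basis or medications that cause an AE will be captured". Its examples of what is left out include one-time and PRN drugs, and it ends: "supportive medications, electrolyte replacement and medications given to treat adverse events will not be captured".

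Other sections provide for drugs that fall in the excluded group:

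- Section 3.3.4, on immune-related events: "Grade 3 to 4: treat with high dose corticosteroids". It also allows moderate-dose steroids for Grade 1 to 2 events. Section 3.3.6.1 gives prednisone courses with tapers of at least one month, and further immunosuppressants such as infliximab and mycophenolate.
- Section 4.1: "Growth factor support is not permitted with exception of administration of filgrastim". Blood products are also provided for there.

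Systemic corticosteroids at entry are an exclusion (Section 2.1.2.8), so an on-study steroid course cannot enter the data as a baseline drug.

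The readouts are a stated secondary objective (Section 1.1.2): "To examine if oral DAC-THU modulates plasma tumor DNA methylation, circulating tumor cells and peripheral immune subsets". Section 5.1.3 names the cell types: "Tregs, MDSC, effector and exhausted CD4+ or CD8+ T-cells, and CD14+ monocytes". T, B and NK subsets are drawn every three weeks (Section 3.4.2). The Treg, MDSC and CTC tubes are drawn before and at completion of each course (Appendix 4). Section 10 plans descriptive statistics and paired non-parametric comparisons before and after treatment, and calls them exploratory.

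**The concern.** Steroids, other immunosuppressants and growth factors can plausibly move the same cell populations that the trial measures as a response to treatment. With no control arm, the before/after pair is the only contrast. A pair whose second sample was drawn on prednisone or filgrastim would enter that contrast unmarked, and Section 5.1.4 then relates CTC change to clinical response. Blood counts are not a named secondary endpoint, but they feed the toxicity summaries and are open to the same distortion from filgrastim and transfusion.

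This is more than missing detail: the plan states a rule that leaves a foreseeable confounder out of the captured data.

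**Working it through.** The plan gives no figure on this point to reproduce. The check sets the sections side by side, then sizes the issue roughly.

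**1. Do exposed patients stay in the sampling?** They can. Section 3.3.6 lets a patient continue DAC-THU while pembrolizumab is held for an immune-related event, so samples can be drawn during a steroid course. How long this lasts also depends on the treatment-delay limits in Sections 3.3.6.2 and 3.6.1.

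**2. Can recorded adverse events stand in for the drug record?** Only in part. Related Grade 2 and all Grade 3 or higher events are generally recorded, with onset and resolution dates. But:

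- the adverse-event fields in Section 8.2 list no treatment given;
- Grade 1 events stay in source (Section 6.1.2.1), although Section 3.3.4 allows steroids for Grade 1 to 2 events;
- a taper of at least a month, begun once the event has improved, can outlast the event dates.

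**3. How many patients might have an immune-mediated event?** Inputs are from the pembrolizumab arm of the Phase III trial tabulated in Section 1.2.10 (N = 154): any grade 45/154 = 29.2%; Grade 3-5 15/154 = 9.7%. Assume these rates apply here. Expected number = n × p, and P(at least one) = 1 − (1 − p)^n.

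| | Expected in 10 | P(at least one in 10) | Expected in 78 |
|---|---|---|---|
| Any grade | 10 × 45/154 = 2.9 | 1 − (109/154)^10 = 96.8% | 22.8 |
| Grade 3-5 | 10 × 15/154 = 1.0 | 1 − (139/154)^10 = 64.1% | 7.6 |

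These are patients with an event at any time on treatment, not samples drawn under steroids. The any-grade figure is the looser bound. The listed immune-mediated entries sum to 62 (a patient can have more than one), and 30 are thyroid events: hypothyroidism 14, hyperthyroidism 12, thyroiditis 4. None of the 30 is Grade 3-5, and Section 3.3.6.1 manages Grade 1-2 hypothyroidism and hyperthyroidism with hormone or anti-thyroid treatment. The entries overlap within patients, so the remaining patient rate cannot be computed. These rates say nothing about filgrastim use.

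**4. Can one pair matter?** Section 10 names no test, so take an exact two-sided Wilcoxon signed-rank test with 10 pairs and no ties.

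- All ten changes in one direction: p = 2/2^10 = 2/1024 = 0.002.
- The same, with only the largest change reversed: the smaller rank sum is 10. Sign patterns with a rank sum of 10 or less number 1+1+1+2+2+3+4+5+6+8+10 = 43, so p = 2 × 43/1024 = 0.084.

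This is a worst case for a single pair. A pair pushed further in a direction it already had would change a rank test little.

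**The case against.** The strongest reply is that nothing is lost. Every drug is in the source documents, and concomitant medications are reviewed weekly in dose finding and every three weeks in expansion (Appendix 3). In a trial of this size steroid dates can be looked up. That stands against any claim that the exposures cannot be separated at all. What remains is that the captured data will not separate them as planned, and that retrieval after the results are known is weaker than a rule set beforehand.

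The analyses are also exploratory, with no threshold or decision resting on them. That limits the weight of the point but does not remove it.

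A reader might infer three further things that the documents do not support:

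- **Acid reducers distort the PK results.** Section 4.4 says "proton pump inhibitors will not be used except on days when DAC-THU is not administered", PK is drawn only on Days 1 and 2 of Cycle 1, and a routine baseline proton pump inhibitor is captured. The only H2-blocker use named comes at the cycle after a Grade 2 infusion reaction. At most, a PRN or newly started acid reducer around those two days is missed.
- **Filgrastim hides neutropenia.** It is not given prophylactically, blood counts are twice weekly in Course 1, and Grade 3 or higher toxicity in the first two cycles not attributable to another cause is a DLT. Filgrastim may shorten an episode but would rarely conceal one.
- **Up to three in ten post-treatment profiles are contaminated.** The 29.2% counts events over the cited trial's whole treatment period, many of them not steroid-treated.

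**Conclusion.** The point holds for the captured data as planned. On-study systemic corticosteroids, other immunosuppressants and filgrastim are kept in source only, and no analysis rule covers samples drawn under them. The before/after immune-subset, CTC and blood-count results therefore cannot be separated from these exposures without going back to source.

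The share of samples affected is unknown. The cited 9.7% to 29.2% is a rough upper bound on steroid exposure by week 10, and it assumes that pembrolizumab-alone rates carry over to the combination. The conclusion also rests on reading *captured* as entry into the study database. Section 6.1.2.2 does not use that word, but the contrast with source documents makes it the natural reading.

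Two limits apply. Full capture would still not separate DAC-THU from pembrolizumab, since every patient receives both. And the primary endpoints, MTD and response, are not shown to be affected. This is a worthwhile, inexpensive improvement to exploratory secondary analyses, not a threat to the trial's main conclusions.

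**What to change.** Amend Section 6.1.2.2 to capture on-study systemic corticosteroids, other immunosuppressants, filgrastim and blood products, with start and stop dates and dose, transcribed from source. Recording dose also lets physiologic steroid replacement be told apart from treatment courses. As a lesser item, note PRN or newly started acid reducers around Cycle 1 Days 1 and 2.

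In Section 10, state that immune-subset, CTC and blood-count samples taken during or shortly after such exposure are flagged, and that the paired before/after analysis is repeated without them. Define the window for *shortly after* before the data are examined; the documents give no basis for a particular length.

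The cost is one short form and one sensitivity analysis. The facts are already in source and concomitant drugs are already reviewed at set visits, so the work is mainly transcription. No clinical rule changes.

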6.2 DATA SHARING PLANS

6.2.1 Human Data Sharing Plan

What data will be shared?

I will share human data generated in this research for future research as follows:

- Coded, linked data in an NIH-funded or approved public repository.
- Coded, linked data in BTRIS (automatic for activities in the Clinical Center).
- Identified or coded, linked data with approved outside collaborators under appropriate agreements.

How and where will the data be shared?

Data will be shared through:

- An NIH-funded or approved public repository, clinicaltrials.gov, dbGaP.
- BTRIS (automatic for activities in the Clinical Center).
- Publication and/or public presentations.

When will the data be shared?

- Before publication.
- At the time of publication or shortly thereafter.

6.2.2 Genomic Data Sharing Plan

Unlinked genomic data will be deposited in public genomic databases such as dbGaP in compliance with the NIH Genomic Data Sharing Policy.

6.3 **RESPONSE CRITERIA**

For the purposes of this study, patients will be re-evaluated for response every 10 weeks (± 1 week). In addition to a baseline scan, confirmatory scans should also be obtained not less than 4 weeks following initial documentation of objective response.

Objective response and progression will be evaluated in this study using the new international criteria proposed by the revised Response Evaluation Criteria in Solid Tumors (RECIST) [(Version 1.1)(109)]. Changes in the largest diameter (unidimensional measurement) of the tumor lesions and the shortest diameter in the case of malignant lymph nodes are used in the RECIST criteria.

Note: Lesions are either measurable or non-measurable using the criteria provided below. The term "evaluable" in reference to measurability will not be used because it does not provide additional meaning or accuracy.

6.3.1 Confirmatory Measurement/Duration of Response

• Confirmation

To be assigned a status of PR or CR, changes in tumor measurements must be confirmed by repeat assessments that should be performed at least 4 weeks after the criteria for response are first met.

• Duration of Overall Response

The duration of overall response is measured from the time measurement criteria are met for CR or PR (whichever is first recorded) until the first date that recurrent or progressive disease is objectively documented (taking as reference for progressive disease the smallest measurements recorded since the treatment started).

The duration of overall CR is measured from the time measurement criteria are first met for CR until the first date that progressive disease is objectively documented.

6.3.2 Definitions

Evaluable for toxicity: All patients will be evaluable for toxicity from the time of their first treatment with DAC/THU/pembrolizumab. Dose limiting toxicities will be assessed during the first 3 weeks of DAC-THU/pembrolizumab therapy.

Evaluable for objective response: Patients who have measurable disease present at baseline, have received at least 9 weeks of DAC-THU/pembrolizumab therapy (one full course), and have had their disease re-evaluated will be considered evaluable for response provided: (1) the patient demonstrates progressive disease or death while on protocol therapy; (2) the tumor is not removed surgically prior to the time complete response or partial response is confirmed; or (3) the patient demonstrates a complete or partial response as confirmed according to protocol criteria. These patients will have their response classified according to the definitions stated below. [Note: Patients who electively terminate therapy before completing 9 weeks of DAC-THU/pembrolizumab therapy and do not expire within 14 days from start of treatment will be replaced. Patients who experience disease progression after 3 weeks of drug therapy but before

completing the minimum of 9 weeks of drug therapy will be taken off-treatment and will only be evaluable for toxicity (not evaluable for response)].

Evaluable Non-Target Disease Response: Patients who have lesions present at baseline that are evaluable but do not meet the definitions of measurable disease, have received at least 8 weeks of DAC-THU/pembrolizumab therapy, and have had their disease re-evaluated will be considered evaluable for non-target disease. The response assessment is based on the presence, absence, or unequivocal progression of the lesions.

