3.1.2 Definition of Dose Limiting Toxicity (DLT)

DLT is defined as:

- Any Grade 3 or greater toxicity that cannot be attributed to a cause other than study treatment during the first two cycles of Course 1 of DAC-THU and/or pembrolizumab therapy such as disease progression or intercurrent illness.
- Any toxicity that cannot be attributed to a cause other than study treatment (DAC-THU and/or Pembrolizumab) that results in study treatment discontinuation.

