3.1.3 Dose Escalation

The revised dosing regimen selected for this trial is based on pharmacodynamic evidence of systemic hypomethylation without significant systemic toxicities mediated by oral DAC-THU in patients with sickle cell disease in a recent Phase 1 clinical trial (108), as well as experience with DAC-THU/Pembrolizumab in NSCLC (Section 1.2.11.2). The frequency of DAC-THU dosing will increase using a conventional 3+3 Phase I study design attempting to maximize systemic DNMT1 depletion while avoiding Grade 3 or greater systemic toxicities (primarily neutropenia/thrombocytopenia). *Due to the uncertainty regarding cumulative toxicities, no intrapatient escalation will be allowed.*

Dose escalation will proceed as indicated in **Table 7** using three patients per dose level (irrespective of Tumor PD-L1 expression) until DLT within the first 6 weeks (two cycles) of DAC-THU therapy is observed. If one of three patients at any given dose level experiences DLT, up to three additional patients will be treated at this dose level. If only one of six patients exhibit DLT, subsequent patients will be enrolled into the next higher dose level. As soon as two patients at any given dose level develop DLT, no additional patients will be entered at that level. Subsequent patients will be accrued into the preceding dose level; if DLT is observed in less than two of six patients treated at this lower level, this dose will represent maximum tolerated dose (MTD).

Table 7: DAC-THU Dosing Schema for High (50% or Greater) and Low (0-49%) PD-L1
Expression Groups

Dose Level	DAC	DAC	THU	THU	Frequency^
	mg/kg/course	mg/kg/day*	mg/kg/course	mg/kg/day*	wk 1,2,4,5,7,8
-1	2.0	0.17	120	10	T;W
1	2.5	0.21	120	10	T;W
2	3.0	0.25	120	10	T;W
*on days a	administered				
^ T: Tuesd	lay; W: Wednesday				

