3.3.5 Dose Modification of DAC-THU

Table 9 lists standard laboratory values that should trigger dose modifications of the investigational drug.

General Adverse Events	Action		
Non-hematological, Grade 1 or 2 (excluding hemorrhage)	 Continue DAC-THU therapy at full dose prescribed. Apply maximum supportive care recommendations. If prolonged duration of Grade 2 adverse event (≥ 7 days) is affecting quality of life, start the next treatment cycle at DL-1. If event persists and continues to affect quality of life for ≥ 7 more days following initial dose reduction, discontinue DAC-THU. 		
Grade 3 ALT and AST	 Hold DAC-THU therapy until recovery to Grade ≤ 1. If ALT and AST resolve to Grade ≤ 1 within 10 days, maintain current dose level. If ALT and AST do NOT resolve to Grade ≤ 1 within 10 days, dose reduce 1 level. If Grade 3 ALT or AST occurs after dose reduction, discontinue DAC-THU. 		

 Table 9: Trigger Values that Result in Dose Modification

General Adverse Events	Action	
Grade 4 ALT and AST	 Hold DAC-THU therapy until recovery to Grade ≤ 1. Resume DAC-THU at DL-1. If Grade 4 toxicities occur after dose reduction, discontinue DAC-THU. 	
Non-hematological, Grade 3 or 4 (excluding ALT, AST, hemorrhage and QT prolongation)	 Apply maximum supportive care recommendations. Hold DAC-THU until recovery to Grade ≤ 1 and resume DAC-THU at the next lower dose level. If symptoms continue to persist at Grade 3 or 4, following dose reduction, discontinue drug. 	
QT prolongation, Grade 3 or 4	 Cardiology consultation will be obtained to determine whether any cardiac functional assessment is warranted or if therapy should be delayed or discontinued. When warranted, ECGs will subsequently be reviewed by the NCI consulting cardiologist. If therapy is continued, dose reduce 1 level for Grade 4 events. If Grade 3 or 4 toxicities occur after dose reduction discontinue DAC-THU. 	
Thrombocytosis	 If platelet count > 500/ mcL but < 1.2M/mcL, continue DAC-THU at current dose. Begin ASA 325mg PO daily. If platelet count 1.2M /mcL or more, hold DAC-THU until platelet count < 1.2 M/mcL, begin ASA 325 mg PO daily and resume DAC-THU at DL-1 if within the first two Cycles of Course 1; or at SAME dose or DL-1 per PI discretion in subsequent cycles. 	
Hemoglobin	• Hgb > 18 g/dL: hold DAC-THU until Hgb WNL. Resume DAC-THU at DL-1.	
Hematological Adverse Events		

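### No rule requires a patient counted as DLT-free in the 3+3 to have completed the DLT window, so non-elective early exits and missed doses can push the MTD upward

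*Combined protocol and SAP*

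**What the plan says.** **Who counts.** Section 6.3.2 gives one toxicity definition: "All patients will be evaluable for toxicity from the time of their first treatment with DAC/THU/pembrolizumab". The next sentence, in the same definition, sets a DLT period: "Dose limiting toxicities will be assessed during the first 3 weeks of DAC-THU/pembrolizumab therapy". The response paragraph of 6.3.2 adds that patients who progress after week 3 and before week 9 "will be taken off-treatment and will only be evaluable for toxicity". It states no replacement for them.

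**The escalation rule.** Section 3.1.3 enters three patients per level "until DLT within the first 6 weeks (two cycles) of DAC-THU therapy is observed", and declares the MTD when fewer than two of six patients treated at a level have a DLT. Section 3.1.2 also uses two cycles for Grade 3 or greater events: "during the first two cycles of Course 1 of DAC-THU and/or pembrolizumab therapy". So 6.3.2 says 3 weeks, while 3.1.2 and 3.1.3 say two cycles, or 6 weeks.

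**What already narrows the gap.** Under 3.1.2, a toxicity not attributable to another cause "that results in study treatment discontinuation" is itself a DLT. A note in 6.3.2 deals with elective withdrawal: "electively terminate therapy before completing 9 weeks of DAC-THU/pembrolizumab therapy and do not expire within 14 days from start of treatment will be replaced". The note sits in the response paragraph and does not say whether the replaced patient leaves the 3+3 count.

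**Dose reductions and interruptions.** Table 9 (3.3.5) tells the site, for a prolonged Grade 2 event affecting quality of life, to "start the next treatment cycle at DL-1". Section 3.3.2 allows interruptions of up to 3 weeks for disease complications or other illness.

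**The concern.** A 3+3 decision rests on three or six patients, so each place should carry a full window of information. Here a place is filled by treatment, not by completing the window. A patient who stops part-way for a reason unrelated to study treatment, with no DLT so far, has told us only about the part observed. Read together, 6.3.2 and 3.1.3 leave that patient in the denominator as a non-DLT.

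The error runs one way: it lowers the apparent DLT rate and makes it easier to clear a level. The MTD is a Phase I primary objective, and 2.3.1 uses it as the dose for all four expansion cohorts. The four further patients at the MTD are meant to confirm safety, but no DLT threshold is stated for them.

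**Working it through.** **1. The plan's own figures.** Section 10 gives up to 6 patients at each of 2 levels plus 4 at the MTD: 2 × 6 + 4 = 16, as stated. The total is 16 + 29 + 23 + 10 + 10 − 10 = 78, also as stated, against a ceiling of 85, which leaves 7. The documents give no operating characteristics for the 3+3, no expected DLT rate and no early-exit rate.

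**2. Which exits leave the window incomplete without a DLT?**
- *Attributable toxicity causing discontinuation:* already a DLT (3.1.2).
- *Elective withdrawal:* replaced (6.3.2), but not tied to the 3+3.
- *Progression:* the sections disagree. Section 6.3.5.1 bars a PD call before the Day 60 evaluation, and 3.1.1 places evaluation at Days 64 and 65 ± 7; a 6-week window ends before either. Yet 3.3.1.1 makes absence of progression a condition for starting each cycle, and 6.3.2 provides for progression between weeks 3 and 9.
- *Symptomatic deterioration* (6.3.5.1, item d), *concurrent serious illness* and *best interest* (3.6.1): open.
- *Interruption of up to 3 weeks* (3.3.2): open; up to half of a 6-week window.

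**3. Illustration.** Assumptions: 6-week window; constant DLT hazard; a fraction f of patients leaves at week 3 and no later DLT is observed in them; true 6-week DLT rate p. The values of f and p are mine.

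- DLT probability by week 3: p₃ = 1 − √(1 − p). For p = 0.40, p₃ = 1 − √0.60 = 0.225.
- Apparent rate: pₑ = (1 − f)p + f·p₃. For f = 0.20, pₑ = 0.80 × 0.40 + 0.20 × 0.225 = 0.365.
- Chance of clearing the level (0/3, or 1/3 then 0/3): (1 − pₑ)³ + 3pₑ(1 − pₑ)² × (1 − pₑ)³.
- At f = 0 and p = 0.40: 0.216 + 3 × 0.40 × 0.36 × 0.216 = 0.309.

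| True 6-week DLT rate | f = 0 | f = 10% | f = 20% | f = 30% |
|---|---|---|---|---|
| 20% | 70.9% | 72.9% | 74.9% | 76.9% |
| 30% | 49.4% | 52.3% | 55.1% | 58.0% |
| 33% | 43.4% | 46.4% | 49.4% | 52.4% |
| 40% | 30.9% | 33.8% | 36.9% | 40.1% |
| 50% | 17.2% | 19.6% | 22.3% | 25.1% |

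Across these rows the rise is about 2 to 9 percentage points.

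**4. Dependence on the window.** With a 3-week window, a patient leaving at week 3 is fully observed, so f drops out and the rise is zero; only exits or missed doses within cycle 1 remain. The window itself matters more. At a 6-week rate of 40%, the chance of clearing is 30.9% if every patient is judged over 6 weeks and 65.3% if every patient is judged over 3 weeks (putting p₃ = 0.225 into the formula above).

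**5. Dependence on follow-up.** Adverse events are documented for 30 days after the last administration (6.1.1). A patient who receives cycle 1 only takes the last DAC-THU dose at about Day 10 (schedule table in 3.1), so follow-up reaches about Day 40. Most of the calendar window is then seen, but without cycle 2 exposure: 4 of the 8 scheduled DAC-THU days (weeks 1, 2, 4 and 5, two days each) and one pembrolizumab dose. The table assumes no later DLT is observed, so it overstates the effect to the extent that follow-up captures one.

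**The case against.** The strongest reply is that no sentence says an early leaver is DLT-free. Being evaluable for toxicity could be meant only for the safety tables, and within 6.3.2 alone a patient who progresses after week 3 has completed that section's 3-week window. Toxicity leavers are DLTs, elective leavers are replaced, PD calls are deferred to Day 60, and 30-day follow-up recovers part of what is missed. The protocol's pembrolizumab PFS medians (1.5 and 2 months in pretreated gastroesophageal cancer, 2.5 to 3.1 months overall in MPM, 3.0 months or more in NSCLC) say little about departures at week 3.

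Most of this stands, and it limits the point. It does not remove it. The DLT sentence sits inside the toxicity definition, 3.1.3 counts patients treated, and nothing sends a non-elective leaver out of the count.

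Three stronger readings are tempting:
- *That early leavers in general count as DLT-free.* The documents do not support this, because toxicity leavers are DLTs and elective leavers are replaced.
- *That the bias is the same whichever window applies.* Step 4 shows that it is not.
- *That every patient dose-reduced without a DLT is wrongly counted and should be replaced.* Reductions for attributable Grade 3 or greater events in the first two cycles are already scored. A reduction deferred to the next cycle falls outside a 3-week window. Removing patients reduced for a drug effect is informative exclusion and could itself bias the MTD upward.

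**Conclusion.** The point holds in a limited form. The plan defines no DLT-evaluable set, and its replacement note is not tied to the 3+3. Non-elective leavers without attributable toxicity, and patients with missed doses, can therefore be counted as non-DLTs on an incomplete window. The direction of bias is upward. Its size cannot be derived from the documents: 3 to 9 points at a true DLT rate of 40% is an illustration under a 6-week window, constant hazard, assumed exit fractions and no later DLT observed. Dose reductions were not modelled. The point should be corrected because the MTD carries into every later cohort and the change is small.

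**What to change.** 1. Reconcile the DLT window: 3 weeks in 6.3.2 against two cycles (6 weeks) in 3.1.2 and 3.1.3. The choice is the sponsor's. Reconcile also the Day 60 rule in 6.3.5.1 with 3.3.1.1 and the early-progression note in 6.3.2.
2. Keep the present toxicity definition for the safety tables. Add a DLT-evaluable set for escalation and MTD decisions: a patient who had a DLT, or who completed the reconciled window with a minimum share of scheduled doses set by the sponsor.
3. State in 3.1.3 that patients who leave or miss doses in the window for reasons unrelated to treatment, without a DLT, are replaced in the 3+3 count, and say whether the elective-withdrawal note applies there.
4. Do not automatically replace patients dose-reduced for a drug effect without a DLT. State in advance how they count, and report them separately at each escalation decision.

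The cost is a few sentences in an amendment, perhaps one to three replacement patients (within the 7 places between 78 and the ceiling of 85), and some escalation time.
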